Cardiac medications prescribed during the initial hospital stay and at the time of follow-up visits must be recorded. Investigators should review all medications carefully at every out-patient clinic visit.

Angina Assessment

The anginal status of the patient will be assessed according to the Canadian Cardiovascular Society (CCS) Classification at all follow-up contacts (calls or visits).

Blood Sampling

Baseline blood samples: Pre catheterization analyses, assessed locally, per standard of care should include:

- Total Cholesterol
- HDL Cholesterol
- LDL Cholesterol
- Triglycerides
- Creatinine
- Hemoglobin
- Glycosylated hemoglobin

Mandatory post PCI or CABG blood sampling will include 12 – 24 hours post index procedure:

- Troponin (and CK and CK-MB if available)
- Hemoglobin
- Creatinine

If elevated, cardiac markers will be measured every 8 hours until they begin to decline. The highest creatinine and the lowest hemoglobin during the hospitalization will be recorded.

At 1, 3 and 5 year follow-up if assessed locally, per standard of care

- Total Cholesterol
- HDL Cholesterol
- LDL Cholesterol
- Triglycerides,
- Creatinine
- Hemoglobin
- Glycosylated hemoglobin

Resource Utilization

Resource utilization data will be collected for each patient at the time of each follow-up contact.

Specific data to be collected will include:

1. Resource use concerning the initial procedure
2. Hospital readmissions
3. Major procedures after the initial procedure
 - revascularization procedures (CABG, PCI)
 - diagnostic procedures (angiography, echocardiography, exercise testing, etc.)
4. Medication
 - Anti anginal medication
 - Medication for treatment of other cardiovascular conditions (hypertension, CHF, arrhythmia)
 - Antiplatelet agents and anticoagulants

Quality of Life Assessment

Data collection will include the completion of the EQ-5D questionnaire prior to the procedure and at the different follow-up time points as indicated in the Follow-Up Schedule.

Working Status

In addition to the quality of life assessment prior to treatment allocation and at all planned clinical follow-up visits, the patient will be requested to provide information relative to his/her working status or any change therein.

7. Reporting of Events

The study will evaluate two different common treatments. For the purpose of this study, only endpoint related events and other possible vascular events are reported.

Trial personnel must report any of the following events within 1 business day of learning of the event.

- Death
- Myocardial infarction
- Cerebrovascular event (TIA, CVA)
- Revascularization (PCI, CABG)
- Bleeding event
- Acute renal failure
- Atrial fibrillation or other arrhythmia
- Rehospitalization

The notification is by preference performed via the electronic CRF (eCRF). Alternatively e-mail or phone may be used for immediate notification, however the eCRF must be completed as soon as possible. Detailed procedures will be listed in the manual of operations. Study personnel must update any follow-up information in the completed adverse event CRF as the event continues and/or resolves. It is the responsibility of the Site Principal Investigator to inform the Institutional Review Board (IRB)/Independent Ethics Committee (IEC) of the adverse event as required by local procedure.

Vigilance Reporting

Since commercially available products are used in this study, reporting relative to device malfunctions must be reported to the relevant manufacturer according to the procedure as defined by the relevant entity.

8. Organization

Sponsor

This is an investigator initiated trial. The Principal Investigators are considered to be the sponsors of this study. The Principal Investigators will be supported by the clinical research organization, Genae, for the financial and logistic aspects of this clinical trial.

Support

The study is supported by research grants provided by Medtronic Corporation and Abbott Vascular.

Steering Committee

The Steering Committee (SC) is the main decision making committee of the trial and has final responsibility for the medical and scientific conduct of the trial. The SC will approve the trial protocol and any amendment (if applicable). The SC further will review all reported adverse events on a regular basis. The Committee may request that the trial be put on hold or even terminated for safety, ethical or other reasons.

The Committee will be comprised of physician-investigators:

- [name], Stanford, CA, USA, Chairperson and Coordinating Clinical Investigator (CCI)
- [name] [name], PhD, Aalst, BE, Co-CCI
- [name] [name], PhD, Eindhoven, NL, Co-CCI
- [name], MD, Glasgow, UK, Co-CCI
- [name], Houston, TX, USA, Co-CCI
- [name], PhD, London, UK, Co-CCI
- [name], Stanford, CA, USA, Co-CCI
- [name], Stanford, CA, USA, Co-CCI

Monitoring

Central clinical and statistical monitoring will be the primary monitoring method of FAME 3 with a commercially available approved device widely used in clinical practice and using techniques outlined by FDA.¹⁶ The Steering Committee believes this risk-based monitoring approach will be effective because the majority of the investigators in FAME 3 are established investigators who have worked with the Principal Investigators in other recent large clinical

randomized trials (FAME 1 and FAME 2). Factors for selection of Investigators include their experience in clinical research and experience with the sponsor or members of the Steering Committee. The Steering Committee also believes this monitoring approach is appropriate because the two treatment strategies being tested are accepted clinical approaches performed routinely; the device being tested (the Medtronic Resolute Integrity/Onyx stent) has a robust safety record in prior human studies; and because the treatment after the initial procedure will be according to routine practice. All sites will enter data or upload electronic records into a secure electronic CRF. Investigators will receive training from the CRO on the protocol and study requirements including data collection and event reporting. The objective clinical outcomes of FAME 3 will undergo central adjudication.

The electronic CRF will not allow randomization into the study unless all inclusion criteria have been met and no exclusion criteria have been met. The CRF will not allow submission unless all of the data elements have been successfully entered. Drop down selections in the electronic CRF will only allow selection of data within a specific expected range for each data point. This will help to eliminate human error in entering data. All sites will electronically upload the signed consent page for each patient enrolled into FAME 3. A minimum of 10% of the CRFs will be randomly selected and monitored to identify inconsistent data, data outliers, and potential protocol deviations that may be indicative of systemic or significant errors in data collection and reporting at a site. If this is identified, targeted on-site monitoring will be conducted. In addition, on site monitoring may occur if the number of adverse events, protocol deviations, subject withdrawals or missed follow-up visits exceeds a pre-defined threshold. Root cause analysis will be performed as necessary to identify appropriate corrective or preventive actions. All adverse events which occur during the study will trigger monitoring which will include review of source documents. Statistical analyses of the entered data will be performed to identify unusual trends, such as too little variance in data at a particular site, too many withdrawals or screen failures, and delays in reporting. Regular videoconferences and email communication will occur between the CRO and the sites to ensure compliance with the above monitoring plan. In person, biannual investigators' meetings will further reinforce the monitoring plan. The monitoring results will be documented and communicated to the Steering Committee by the CRO on a quarterly basis or more frequently, as necessary. The Steering Committee will provide reports to FDA as requested.

Investigator responsibilities

As this is an investigator Initiated Clinical Trial, it is expected that each involved investigator is responsible for obtaining the relevant approvals and to provide the required reporting throughout the trial.

Clinical Events Committee

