Key Secondary Endpoint	Death, MI, and stroke will be evaluated at 3 years, where subjects contribute data from time of enrollment until the occurrence of one of the above events or three year follow-up, whichever occurs first. Subjects who die or are lost to follow up before this time will be censored at their last recorded activity.
Statistics	The study will use a noninferiority design. For the primary endpoint, assuming 12% of subjects experience MACCE in the CABG arm by 1 year post randomization, given a clinically irrelevant hazard ratio of 1.65, a one-sided 2.5% significance level and 90% power to reject the null hypothesis if it is false, the sample size necessary is 645 patients per group (1290 for the entire study). To account for loss to follow-up and subject withdrawal, up to 1500 patients will be enrolled from 50 sites.
Principal Investigators	[name] (PI), [name] [name], PhD (Co-PI) and [name] [name], PhD (Co-PI)
Steering Committee	[name], [name] [name], PhD, [name] [name], PhD, [name], [name], [name], [name], [name].
Clinical Events Committee	[name], (Chair) Stanford University Medical Center ██████████, MD, Duke University Medical Center ██████████, MD, Duke University Medical Center ██████████, MD, Stanford University Medical Center
Data Safety Monitoring Board	██████████, MD, (Chair) University of California, Irvine ██████████, MD, New York Presbyterian Hospital/Weill-Cornell Medical Center ██████████, MD, UCLA Medical Center
Statistical Analysis	[name], Quantitative Sciences Unit, Stanford University Medical Center
FFR Core Lab	Stanford University Medical Center
Angiography Core Lab	Stanford University Medical Center
Economic and Quality of Life Analyses	[name], Department of Health Research and Policy Stanford University Medical Center
Clinical Research Organization	genae
Sponsor(s)	Investigator Initiated Trial, with Leland Stanford Jr. University as the official Sponsor.
Support	Study is supported through research grants by Medtronic Corp. and Abbott Vascular.

2. Summary of Investigational Plan Changes

Revision History	Effective Date
1.0	28Feb2014
2.0	15May2015
2.1	15Jun2016
3.0	27Feb2018

Version 2.0, 15May2015

Section	Change From	Change To	Rationale for Change
1.0 Protocol Summary table, Steering Committee		Added Steering Committee members [name] and [name]	Updated to include new Steering Committee members that agreed to participate after initial CIP version.

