- If the FFR in a vessel is ≤ 0.80 , the operator is not obligated to stent. For example, if on pullback of the wire, diffuse disease is diagnosed without an obvious focal step-up, stenting is not mandated. Or if a small sidebranch of a bifurcation lesion has an FFR ≤ 0.80 , stenting is not mandated. In other words, operators should use their good clinical judgment and follow their routine practice.
- In case of serial stenoses, FFR “of the complete vessel” should be ≤ 0.80 to warrant PCI of one of more of these stenoses. Long stents to cover a segment or multiple shorter stents, can be placed at the discretion of the operator. After treating one stenosis, FFR should be remeasured to determine whether the second stenosis warrants therapy.
- In the case in which the operator decides to revascularize a chronic total occlusion, FFR measurement is not mandatory and a default FFR value of 0.50 can be applied.
- It is strongly advocated to measure the final post DES implantation FFR, to document the degree of resolution of the pressure gradient achieved by the revascularization. A pullback should be performed to address the source of any residual gradient and to check for drift in the pressure wire.
- Based on the literature and clinical experience, we expect a $<1\%$ complication rate from FFR measurement.¹⁵

PCI Strategy:

- PCI will be performed solely with the Medtronic Resolute Integrity/Onyx stent. If the Resolute stent cannot be delivered, an alternative current generation drug-eluting stent can be substituted, preferably an everolimus eluting stent.
- Covering the entire diseased portion of the lesion with a single drug-eluting stent is recommended.
- A single cross-over stent strategy for bifurcation lesions is recommended, with provisional sidebranch stenting only if < TIMI 2 flow is persistent after kissing balloon inflation of the sidebranch.
- It is not recommended to revascularize a chronic total occlusion (CTO) unless a patient has persistent symptoms after the initial PCI, documented ischemia on noninvasive testing involving the region subtended by the vessel with the CTO, and visible collaterals which fill a vessel >2.5 mm in diameter. If the operator is considering bringing the patient back for revascularization of a CTO, this should be documented in the CRF at the time of the baseline procedure. The operator is not obligated to bring the patient back, but this will avoid confusion regarding whether or not the follow-up procedure is planned.

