- PCI may be staged if necessary, but this is not encouraged. The plan to stage the PCI of a particular lesion should be declared before instrumenting the lesion and can be contingent upon the patient having persistent symptoms. The second portion of the PCI procedure should be performed within four weeks of the first portion.

Medications

Type of medication	CABG	FFR-guided PCI
Aspirin 80-100 mg once a day for the duration of the study	Pre- and post-procedure	
High dose statin (e.g., atorvastatin 80 mg)	≤ 24 hours before the procedure	
Clopidogrel or its equivalent (i.e. prasugrel or ticagrelor) ² for 6 months (12 months recommended)	-	Pre-loading with 600 mg or equivalent
Bivalirudin for anticoagulation	-	Recommended
Beta blockers or amiodarone to prevent atrial fibrillation	At site's discretion	

For patients who require anticoagulation, single antiplatelet therapy is acceptable		
---	--	--

¹ Ticlopidine should not be used.

Follow-up

Patients will be seen and evaluated at 1 month (± 7 days), and 1, 3 and 5 years (± 30 days) after the index procedure with the specific assessments as outlined in the follow-up table below. . Phone call follow-up will occur at 6 months and 2 years . One month is defined as 30 days (i.e. 6 months equals 180 days). Each year will be defined as 360 days. During follow-up patients will be assessed for any MACCE, angina severity, and quality of life (EQ-5D).

Follow-Up Schedule

	Base-Line	12-24 Hours Post Proc.	Dis-charge	1 month (± 7 days)	6 month (± 30 days)	1 year (± 30 days)	2 years (± 30 days)	3 years (± 30 days)	5 years (± 30 days)
	Hosp.	Hosp.	Hosp.	Visit	Call	Visit	Call	Visit	Visit
Medical History	X								
QOL (EQ-5D)	X			X		X		X	X
Working Status	X			X	X	X	X	X	X
ECG	X	X ¹	X	X		X		X	X
Lab Studies	X	X ¹	X			X		X	X
Cardiac Medications	X		X	X	X	X	X	X	X
Resource Utilization			X	X	X	X	X	X	X
MACCE			X	X	X	X	X	X	X

¹ The 12-24 hour assessment is sufficient in case discharge is within 36 hours post-procedure

Recording of Adverse Events

For the purpose of this trial, only MACCE events will be reported. In case a patient does not attend the final visit, all efforts should be made to obtain a complete inventory of these events.

Electrocardiography

Twelve lead electrocardiograms (ECGs) are recorded before the procedure (within 24 hours), 1 day after the procedure (12 to 24 hours post procedure) and at discharge³, 1 month, 1, 3 and 5 years post index procedure.

Recording of Cardiac Medication

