Recently, the EXCEL¹⁸, NOBLE¹⁹ and BEST²⁰ trials have been published. These studies demonstrate a one year MACCE rate which is in the 10% or lower range in the CABG arm, compared with the SYNTAX and FREEDOM trials which were in the 12% range. In addition, in EXCEL, a clinically acceptable non-inferiority margin for death, CVA and MI was a hazard ratio in the 1.4 range. Because of the lower event rates after CABG in more recent studies and because we will also be including revascularization as part of MACCE, the Steering Committee feels a hazard ratio of 1.65 is more appropriate for defining a clinically acceptable non-inferiority margin. We assume a 10% of subjects in the CABG arm experience MACCE, and further that patients in the PCI arm will not experience a higher rate than those in the CABG arm. We would deem an increase in event rate up to and including a 16% event rate as not clinically inferior. Thus, given a clinically irrelevant hazard ratio of 1.65, a one-sided 2.5% significance level and 90% power to reject the null hypothesis if it is false, the sample size necessary is 645 patients per group (1290 for the entire study). These calculations are based on assumptions of uniform accrual over time, no loss to follow-up, exponentially distributed death times, and a Wald test statistic. Thus, to account for patients lost to follow-up and subject withdrawal we will enroll up to 1500 patients from up to 50 medical centers.

Sensitivity Analyses

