Detection of rise and/or fall of cardiac biomarkers (CK-MB or troponin) with at least one value above the 99th percentile of the upper reference limit (URL) together with evidence of myocardial ischemia with at least one of the following:

- Symptoms of ischemia
- ECG changes indicative of new ischemia [new ST-T changes or new, persistent, non rate-related left bundle branch block (LBBB)]
- Development of pathological Q waves (≥ 0.03 seconds in duration and ≥ 1 mm in depth) in ≥ 2 contiguous precordial leads or ≥ 2 adjacent limb leads of the ECG
- Imaging evidence of new loss of viable myocardium or new regional wall motion abnormality

PCI or CABG-related MI (<72 hours after PCI or CABG):

Elevation of the cardiac troponin value $> 10 \times 99^{\text{th}}$ percentile of the URL in patients with a normal baseline reference level, or an increase of $> 20\%$, if the baseline values are elevated, but are stable or falling. In addition, at least one of the following:

- (i) new pathologic Q waves or new left bundle branch block
- (ii) angiographic documented new graft or new major native coronary occlusion
- (iii) imaging demonstration of new loss of viable myocardium or new regional wall motion abnormalities is required.

Stroke (cerebrovascular accident or CVA) is the rapid onset of a focal or global neurological deficit. If the duration is <24 hours, the event is deemed a transient ischemic attack (TIA), except if an intervention is performed as defined below. If the duration is ≥ 24 hours, it is deemed a stroke. Stroke is subdivided as ischemic, hemorrhagic, or undetermined. Ischemic stroke refers to acute symptomatic episode of focal cerebral, spinal, or retinal dysfunction caused by an infarction of the central nervous system tissue. Hemorrhagic stroke is an acute symptomatic episode of focal or global cerebral or spinal dysfunction caused by nontraumatic intraparenchymal, intraventricular or subarachnoid hemorrhage. Undetermined stroke is one with insufficient information to allow categorization as either of the above two.

Stroke is diagnosed when the following criteria are met:

1. Rapid onset of a focal/global neurological deficit with at least one of the following:
 - Change in level of consciousness
 - Hemiplegia
 - Hemiparesis
 - Numbness or sensory loss affecting one side of the body
 - Dysphagia/aphasia
 - Hemianopia
 - Amaurosis fugax
 - Other new neurological sing(s)/symptom(s) consistent with stroke

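### No troponin is required after a planned second PCI session, so procedure-related MIs could be under-counted in the PCI arm only; the fix is cheap and the size of the effect is unknown

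*Combined protocol and SAP*

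**What the plan says.** - **Troponin.** Section 6, Blood Sampling: "Mandatory post PCI or CABG blood sampling will include 12 – 24 hours post index procedure". Elevated markers are then repeated every 8 hours until they fall.
- **ECG.** Section 6, Electrocardiography, sets a tracing "1 day after the procedure (12 to 24 hours post procedure) and at discharge". The 12–24 hour tracing refers to the procedure in the singular, without the word index. The Follow-Up Schedule has one 12–24 hour post-procedure column and none for a second session.
- **Second sessions.** Section 6, PCI Strategy, permits staging but discourages it: "The second portion of the PCI procedure should be performed within four weeks of the first portion". For occlusions it adds: "If the operator is considering bringing the patient back for revascularization of a CTO, this should be documented in the CRF". The CABG section describes no staged counterpart.
- **Endpoint.** Appendix A defines "PCI or CABG-related MI (<72 hours after PCI or CABG", which is not limited to the index procedure. It needs a troponin rise plus new Q waves or left bundle branch block, an angiographic occlusion, or an imaging finding. Under the repeat revascularization definition, planned staged PCI is not an event.

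**The concern.** The endpoint definition and the data schedule do not match. The definition counts an MI after a planned second PCI session; the schedule does not require the measurement that would identify it. A site can follow the schedule exactly and hold no troponin from that session.

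The gap lies essentially in one arm. Unplanned later procedures also have no required sampling, in either arm, but they are already MACCE as repeat revascularizations, so a missed MI there does not remove the patient from the primary event count. A planned PCI session has no such backstop. Any loss lowers the PCI event count and favours the trial's claim. The 3-year death, MI and stroke comparison shifts in PCI's favour in the same way.

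**Working it through.** **1. The plan's own figure.** Section 10 works from "given a clinically irrelevant hazard ratio of 1.65, a one-sided 2.5% significance level and 90% power to reject the null hypothesis" and "We assume a 10% of subjects in the CABG arm experience MACCE".
- Events = 4 × (1.960 + 1.282)² / (ln 1.65)² = 167.6.
- PCI rate at the margin = 1 − 0.90^1.65 = 15.96%; mean of the two arms = 12.98%.
- Patients per arm = 167.6 / (2 × 0.1298) = 645.7, which reproduces the stated 645.

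The Protocol Summary instead has "assuming 12% of subjects experience MACCE in the CABG arm by 1 year post randomization". The same formula with 12% gives 540 per arm (PCI at 1 − 0.88^1.65) or 698 (12% in both arms), so 10% is used below.

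**2. Inputs for the loss.** The documents give no share of PCI patients staged, no procedure-related MI rate per second session, and no share missed without required testing. All three are assumptions. The only anchor is Section 3: 5.7% for all MI over one year in the FFR-guided arm of the earlier FAME trial.

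**3. Formulas.** Evaluated at a true hazard ratio of 1.65, with 750 per arm (the maximum of 1,500 enrolled):
- Loss = share staged × MI rate × share missed
- Observed PCI rate p = 0.1596 − loss
- Observed HR = ln(1 − p) / ln(0.90)
- SE = √(1/75 + 1/(750p))
- One-sided error = Φ(ln(1.65/HR)/SE − 1.96)

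Example, 20% staged, 2% MI, three quarters missed: loss = 0.0030; p = 0.1566; HR = 1.616; SE = √(1/75 + 1/117.4) = 0.148; error = Φ(0.14 − 1.96) = 3.4%.

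| Staged | MI rate | Missed | PCI events lost | Observed HR | One-sided error |
|---|---|---|---|---|---|
| none | – | – | 0 | 1.650 | 2.5% |
| 5% | 1% | half | 0.2 | 1.647 | 2.6% |
| 10% | 2% | half | 0.8 | 1.639 | 2.8% |
| 10% | 2% | all | 1.5 | 1.627 | 3.1% |
| 20% | 2% | three quarters | 2.3 | 1.616 | 3.4% |
| 20% | 3% | all | 4.5 | 1.582 | 4.7% |
| 30% | 5% | all | 11.3 | 1.482 | 10.6% |

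At 645 per arm the results are close: 3.4% for the 20%/2% row and 9.7% for the last.

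**4. Break-even.** Doubling the error to 5% takes a loss of 0.67 percentage points at 750 per arm (5.0 events), or 0.72 points at 645 per arm (4.7 events).

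**5. Overlap.** The table treats every missed MI as a lost MACCE patient, although some would have another event within the year. If the two are independent, the loss shrinks by the factor 1 − 0.16 = 0.84. The 20%/3% row then has loss 0.006 × 0.84 = 0.0050 and error 4.2%. If half of those MIs are also detected locally, the loss is 0.0025 and the error 3.3%.

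**The case against.** The case against a serious problem is substantial, and much of it stands.

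- **The ECG wording is not explicit.** Only the troponin rule names the index procedure. For the 12–24 hour ECG the defect is ambiguity. An ECG is also due at 1 month ± 7 days (days 23–37), around or after most sessions staged within four weeks. It may show new Q waves, but the schedule has no laboratory tests at that visit, so it cannot satisfy the definition alone.
- **Other routes into MACCE exist.** Besides death and stroke, unplanned revascularization and spontaneous MI after 72 hours both count, so an occlusion that leads to unplanned reintervention is captured without a troponin.
- **The definition is strict.** It needs supporting ECG, angiographic or imaging evidence, and many such events would prompt local testing, which nothing forbids. MI and rehospitalization must be reported within one business day, and adverse events trigger source review. The manual of operations and the Clinical Events Committee's rules are not in the documents and may say more.
- **Second sessions may be few.** Staging is discouraged, CTO treatment is restricted, and patients with more than one chronically occluded major vessel are excluded.

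These safeguards depend on someone recognising an event. Reporting runs from when staff learn of it, and the committee adjudicates events for which the minimum data exist. None of them supplies a troponin that was never drawn. A reader might infer that these MIs go largely unmeasured; the documents show only that their measurement is not required.

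**Conclusion.** The point holds as a worthwhile, inexpensive improvement. The mandatory troponin covers the index procedure only, planned second sessions belong to the PCI strategy, and an MI there is a MACCE that cannot be established without a troponin. Possible under-counting is therefore confined essentially to the PCI arm, and its direction is toward non-inferiority.

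The size is not known. Low-to-middle assumptions (5–20% staged, 1–2% MI, half to all missed) give a one-sided error of about 2.6–3.4% against 2.5%. About five missed PCI events would double it.

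A reader might go further and infer that the primary test is materially biased, citing the last row of the table. The documents do not support that. A 5% missed rate at a single partial session is close to the 5.7% that the earlier FAME trial recorded for all MI over a full year, and the calculation ignores overlap with other events.

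**What to change.** In Blood Sampling, Electrocardiography and the Follow-Up Schedule, require the existing 12–24 hour troponin and ECG after the index procedure and after every planned staged or CTO PCI session, with the same repeat-marker rule. Send the results to the Clinical Events Committee under the existing <72 hour definition. The endpoint definition and sample size stay as they are.

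For sessions already done, report by arm the number of planned second sessions and the share with a troponin, and add a sensitivity analysis that assigns MIs to untested sessions over a stated range of rates.

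The cost is one troponin and one ECG per second session, amendment wording and one eCRF page. The change may add a few PCI-arm events, and so makes non-inferiority slightly harder to show.
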